#### Additions for participants with an obstructing stone

- A urine culture will be ordered for all subjects undergoing treatment to evaluate for the definitive presence of infection in follow-up.

Follow up – Routine Care: As part of the routine treatment patients may be asked to strain their urine and retain stones. Patients may also be prescribed alpha blockers to facilitate stone passage, as well as pain medications to take as needed. Surgical (SWL and URS) participants will also be seen for an ultra-low-dose CT, plainfilm KUB and/or renal ultrasound exam post treatment, as standard care.

Follow up – Investigative –Subjects Undergoing Ultrasonic Propulsion or Enrolled in a Control Group: Research staff will contact the patients each week for three weeks and review their charts each week for the longer of a) 90 days or b) follow-up imaging has been completed to

assess for acute colic events, stone passage, and/or additional interventions/adverse events. Subjects will be asked to record the date of any stone passage since the investigational study. Pain medication taken by the participant will be recorded and converted to Morphine equivalents. With the exception of subjects who underwent the investigational study prior to their surgical treatment, all subjects will be scheduled for follow-up visit if it is not already prescribed as part of their routine care. The subject will be scheduled either for a low dose CT, plainfilm KUB, ultrasound, or a combination of KUB and ultrasound as follow-up. In the case of multiple study treatments, the subject will undergo only 1 follow-up CT; ultrasound and/or plainfilm KUB will be used for any additional follow-up requirements. A certified letter will be sent to any subjects lost to the three week follow-up or post-study imaging visit. The letter will be sent if the subject cannot be reached within four weeks following the study.

In addition, specifically for participants with an acute obstructing stone, subjects will be telephoned with the results of the urine culture test when infection is indicated. This may occur through standard-of-care or by the research team.

For those subjects with residual fragments recruited into the long-term clinical follow-up study, subjects will be contacted semi-annually for up to 3 years and charts reviewed semi-annually for up to 5 years following the investigative study. A subject is considered to have completed the study once the 5-year period has passed or if the subject undergoes a kidney stone procedure as part of their standard-of-care stone management on the same side as enrolled for this study. The reasons why subjects exit either the treatment or control group of the study will be recorded. Potential reasons include treatment failures, lost to follow up, withdrawal, end of study, and death. Subjects who exit the study for surgery resulting from the residual fragments will be adjudicated as treatment failures.

A second blinded physician, radiologist, sonographer, or equally qualified individual will be used to review the ultrasound images and confirm representative documented stone movement.

### **1.3 Study Analysis**

Safety will be determined by the frequency and severity of any adverse events. Effectiveness of the device will be measured by the % of stones moved and average distance of stone motion. The frequency of stone motion in the desired direction (i.e. toward the UPJ or away from the UPJ) will also be assessed. For the observation/medical expulsive therapy population (1a) and stone fragment population (3), the time between treatment and any reported stone passage will be an additional effectiveness parameter. For the obstructing stone population (4), change in pain status and hydronephrosis status, in addition to time between treatment and any reported stone passage, will be additional effectiveness parameters. Sub-categories will include the average number of pushes and the average treatment time.

Safety of ultrasonic propulsion: Safety is a difficult parameter to establish, particularly for the obstructing stone population who are already experiencing symptoms and subjects receiving SWL and URS treatment, since both these procedures may result in potential confounding

complications (see Table 2). In addition, all patients, at any time, could experience complications associated with the natural passage of a stone, such as renal colic, irrespective of having received our investigational treatment.

A method for evaluating complications associated with the investigational study is listed in the bullet points below. Adverse events (AEs) that occur during or after the study will also be subdivided into procedure AEs and device AEs. Procedure AEs are defined as morbidity / mortality events that may occur no matter what device is used. Examples include heart rate changes during treatment, anesthesia issues, discomfort from lying on an exam table, or for this case, intermittent urinary obstruction and other pain events associated with kidney stones. Examples of device AEs include irritation where the probe was in contact with the skin or an AE that occurs as a result of a software issue.

- The number and level of procedural and device AEs identified during and after the investigational procedure will be established.
- The number and severity level of the AEs will be compared with potential occurrences with routine care.
- Medication use will be reported for each subject. The results will be compared against the baseline level of pain medication used by the general stone population that falls within the same treatment group.
- Short-term complications (within 90 days) identified from follow-up contact and medical chart reviews will be recorded including type and frequency. The results will be compared to the types and frequency of complications expected in stone patients on average.
- The presence and degree of hydronephrosis will be compared between the research study visit and follow-on clinical visit. The result will be compared to stone patients on average.

Effectiveness of ultrasonic propulsion: The pre- and post- ultrasound images, video data, and manual data recorded during each push pulse will be used to evaluate stone motion. The motion associated with each push will be categorized based upon the following criteria: 1) no motion, 2) moved but trapped within a confined space, such as a calyx, 3) translation of the stone to a new location, or U) unintended activation of the Push pulse. The distance achieved for motion #3 and an estimate of the total distance moved for the entire treatment will also be determined. Lastly, the anatomical position of each stone will be identified. From these data, quantitative measurements can be made as to the effectiveness of the clinical device in moving stones. The analysis can be made over all subjects, but also broken down based on group, stone location, or stone size groupings.

- % occurrence of each motion level achieved per total number of pushes
- % occurrence of each motion level achieved as a function of anatomical location.
- Average distance moved for motion levels 3
- Total distance moved per stone

- For subjects enrolled in the long term study, % occurrence of clinical stone events and length of time to those events from the investigative study.

Stone Passage: Stone passage will be identified either from the subject urine screen, chart review, or post-treatment imaging compared to pre-treatment imaging. If the stone was captured and sent for stone analysis, the size and type of stone will also be documented.

- The number of ultrasonically treated stones that passed (spontaneously without additional surgical procedures) will be reported.
- If available, the time between the investigational ultrasonic intervention and stone passage will be recorded.

Metrics for Success: The following metrics will be used as a measure of success for an individual study.

- By any measure, the stone moved more than 2 mm.
- The treatment procedure was tolerable to the patient.
- No complication requiring intervention beyond that typically experienced with routine care.
- Decrease in pain, hydronephrosis, or absence of emergency intervention in the 3-week post study follow-up period.

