**Date: 30 March 2022**

**Revised Clinical Trial Protocol**  
**Safety and Effectiveness of Ultrasonic Propulsion of Kidney Stones –**  
**a feasibility study**

This is an unblinded, first-in-human, early feasibility study, with one randomized component. conducted within the University of Washington medical system in conjunction with the Department of Urology and the Division of Emergency Medicine, and the Puget Sound Veterans Affairs Health Care system in conjunction with the Division of Urology.

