**UWMC Kidney Stone Center (KSC)**  
**Puget Sound VA Urology Clinics**

**Changes Implemented: upon approval from FDA**

**STUDY OBJECTIVES**

**Primary**

Demonstrate the ability to reposition stones within the human kidney collecting system using the Propulse 1 device.

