**Table 1: Planned Recruitment Information**

Subject Population	# Subjects Consented but Screen Fail	# Subjects Control Arm	# Treatment Cases*
FIH	5	0	15
URS	9	0	18
RCT	41	42	42
Acute	30	0	22
De Novo	0	0	5
Dislodging	15	0	20

\* The Number of individual subjects treated will not exceed 117. This column exceeds 117 and the consented column exceed 259 because at least 5 subjects have been recruited across multiple study populations and are therefore counted twice.

Inclusion Criteria Population Groups 1 through 3:

- Individuals suspected of having at least one kidney stone. This includes:
  - Patients who are being managed with watchful waiting or medical therapy
  - Patients who recently underwent treatment of their stone with SWL or URS.
  - Patients scheduled for SWL or URS treatment

Inclusion Criteria Population Group 4:

- Individuals suspected of having an obstructing stone. This includes:
  - Patients presenting with renal colic
  - Patients presenting with hydronephrosis or dilation of the ureter

Exclusion Criteria Population Groups 1 through 3:

The following subjects will be excluded from this study:

- Individuals under 18 years of age
- Individuals with stones that are not visible with ultrasound
- Individuals not available for follow-up or unwilling to do follow-up
- Individuals with a coagulation abnormality or taking blood thinners or other anticoagulants at clinically significant levels.
- Individuals with mobility issues who are unable to comfortably lie for up to 30 minutes or roll from their back to their side
- Individuals belonging to a vulnerable group (pregnant, mentally disabled, physically disabled, prisoner, etc.)
- Individuals who have already received four previous ultrasonic propulsion treatments
- Individuals who have received an ultrasonic propulsion treatment within the last month (4 weeks)

Exclusion Criteria Population Group 4:

In addition to all the exclusion criteria listed above for population groups 1 through 3, the following subjects will be excluded from this study:

- Individuals with a suspicion of kidney infection or exhibiting signs of sepsis
- Individuals whom the treating physician considers to be at high risk for serious alternate diagnoses such as acute infectious etiologies (e.g. cholecystitis, appendicitis), aortic aneurysm and rupture, or bowel disorders.
- Individuals who have undergone renal transplant, or individuals who will undergo dialysis.
- Individuals with bilateral hydronephrosis

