Study Treatment – Investigative – All Subjects: The investigational examination is expected to take 30 minutes to 1 hour and will be performed by either a certified sonographer or physician identified as an investigator for this study and previously trained on the device. The study will take place after consultation with at least one urologist and with at least one physician in attendance.

- a) Prior to the ultrasound study, participants will complete a baseline pain questionnaire.
- b) A photo of the subject's skin in the region where the probe will be positioned will be taken.
- c) Participants will undergo a diagnostic ultrasound examination by a certified physician or sonographer with the investigational device. The sonographer and physician will verify the stone is visible on ultrasound and near the location identified on the most recent diagnostic imaging, if available.

- d) Audio and video of the exam will be recorded. Select images of the kidney anatomy and stone will also be captured using the screen capture functionality of the investigational software. A second photograph of the skin in the region where the probe was positioned will be taken between the screening examination and stone pushing.
- e) Participants will undergo stone pushing with the investigational device. The operator will begin with low output and increase the output as necessary. The subject will be directly asked if they experienced any sensations with each of the first three pushes. The subject will be advised to report if they feel any change in sensation with the remainder of the study – they will no longer be asked directly. A maximum of three pushes should be attempted from a single probe position and focus. If the stone does not relocate, the operator should alter the angle of approach by (first) rotating the probe to a new angle of approach, (second) repositioning the probe, and (last) repositioning the subject for a more optimal transducer to stone angle (i.e. so as to not push the stone against the tissue wall.)

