- f) The study staff will monitor the real-time ultrasound image during each burst applied. If echogenicity related to cavitation within the tissue is observed, the treatment will be paused for 1 minute. The treatment will resume at a reduced dose level. This procedure will be repeated as echogenicity related to cavitation in the tissue is continued to be observed. If the treatment setting is reduced to 50 W/cm^2 and cavitation is still observed, the study will be stopped.
- g) Select ultrasound images extending over the duration of the Push and a listing of the system settings, including the target location and Push power, will be recorded automatically to the system hard drive. The output voltage, patient position, stone position, and result of the Push burst will also be recorded manually. There are three potential types of motion for each push pulse, 1) no motion, 2) moved but trapped within a confined space, such as a calyx, 3) translation of the stone to a new location. A fourth option that can be recorded is U) unintended Push. This occurred occasionally with the animal studies through accidental activation of the touch screen.
- h) With Probe 1 (C5-2 transducer) a maximum of 120 Push bursts will be delivered in a single session and a maximum of 40 Pushes will be delivered to a single location. With the SC-X probe, a maximum on-time of 5 minutes will be delivered in a single session. If the operator switches probes, the sum of the percentage of the limits of use for either probe cannot exceed 100% (e.g., 90 pulses with the C5-2 probe is 75% of the total 120, so 25% of the 5 minute total, or 1 minute 15 s total ON time could be used with SC-X.)
- i) Participants will immediately undergo a second diagnostic ultrasound exam to confirm the location of the stone after treatment. Audio and video of the exam will be recorded and select images of the kidney anatomy and stone will also be captured.
- j) A third and final photograph of the skin in the region where the probe was positioned will be taken at the conclusion of the investigational study.
- k) Participants will complete a second questionnaire at the completion of the exam addressing any discomfort or pain they may have felt related to the procedure.

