- l) The subject may be provided with a strainer to collect stones during the three week follow-up period. In some investigational procedures passing a stone is unlikely and not relevant to the study so no strainer will necessarily be provided. The subject may also be provided with a medical diary sheet to record their medication use during the three week follow-up period. The diary is a copy of clinical research form 6B.
- m) The subject may be provided with subsidized parking pass for the duration of the research study.
- n) The subject may be provided with bottled water throughout their stay for the research study to help with hydration.

The study will cease immediately if the participant requests that the study end or if the participant experiences significant pain and/or discomfort. If at any point the participant expresses some level of discomfort, the source of the discomfort will be identified, recorded, and resolved if possible. The operator will use the usual safety procedures for operating a clinical diagnostic ultrasound instrument, including using the ALARA principle.

Exceptions for the URS participants receiving treatment during the surgical procedure.

- a) The subject will not complete a baseline pain questionnaire because the investigation procedure will be completed with the subject under anesthesia.
- d) The subject will not be asked if they feel any sensation related to the push as they will be under anesthesia.
- d) The subject will not be moved to any new scanning positions once the URS guide is inserted.
- g) The subject will not be given a post-study pain questionnaire since they will not be awake and accessible for several hours (after recovery). This is not a relevant timeline for obtaining this information; the questionnaire should be delivered immediately following the procedure.

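### The 2 mm success rule, the share of stones moved and total distance per stone can count motion caused by repositioning the patient rather than by a Push

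*Protocol*

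**What the plan says.** The primary objective reads: "Demonstrate the ability to reposition stones within the human kidney collecting system using the Propulse 1 device". The opening description of the design is "This is an unblinded, first-in-human, early feasibility study, with one randomized component". That randomized component is the post-lithotripsy population, and no sham session or other comparator is described for stone repositioning.

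Section 1.2 step e sets an order for a stone that does not relocate: rotate the probe, then move it, and finally "last) repositioning the subject for a more optimal transducer to stone angle". The exclusion criteria in section 1.1 fit this, since they rule out people who are "unable to comfortably lie for up to 30 minutes or roll from their back to their side". For patients treated during ureteroscopy (URS), section 1.2 makes an exception: "The subject will not be moved to any new scanning positions once the URS guide is inserted".

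Step g covers recording. Images spanning each Push are saved automatically, and "The output voltage, patient position, stone position, and result of the Push burst will also be recorded manually". Step i adds: "Participants will immediately undergo a second diagnostic ultrasound exam to confirm the location of the stone after treatment". It does not ask for the same posture or scan plane as the first exam.

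Section 1.3 measures effectiveness by the percentage of stones moved and the average distance of motion. Its sources are pre- and post-treatment images, video and the manual record of each Push. Each Push gets a motion category and level 3 motions get a distance. In addition, "an estimate of the total distance moved for the entire treatment will also be determined", and total distance per stone is a listed outcome. The motion metric of success for an individual session is movement above 2 mm by any measure at all.

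**The concern.** The protocol plans a change of posture within the session, and plans it for stones that pushes have so far failed to relocate. When a patient rolls, a loose stone or fragment may shift. Even a fixed stone may appear to have shifted, because the scan plane is new. Neither displacement is an effect of the device.

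The 2 mm metric does not require the movement to occur during a Push. Nothing ties the percentage of stones moved to push-time motion, and total distance over the treatment has no calculation rule. All three can therefore absorb motion that arises between pushes. The error runs in the device's favour, because it enters where the device has not yet worked and can turn a failed session into a successful one. With no comparator for repositioning, background motion cannot be estimated and subtracted.

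**Working it through.** The protocol states no hypothesis, error rate, standard deviation or expected distance for stone motion, so there is no figure to reproduce. The check is a comparison of outcomes with the text, followed by simple arithmetic on exposure.

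**Which outcomes are open to motion between pushes (section 1.3)**

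1. Percentage of each motion level per total pushes, and the same by anatomical location: tied to a Push. A roll is not a Push, so these are largely protected.
2. Average distance for level 3 motions: tied to a categorized Push, so largely protected.
3. Total distance per stone: an estimate over the whole treatment. The text does not say whether it sums per-push distances or compares start with end. Open.
4. Percentage of stones moved: no definition of a moved stone, and pre/post images are an admitted source. Open.
5. The 2 mm success metric: any measure suffices, so a pre/post comparison across a posture change satisfies it as written. Open.

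**How many cases could be exposed (Table 1)**

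- Planned treatment cases: 15 + 18 + 42 + 22 + 5 + 20 = 122. This agrees with the footnote to the table: 117 individuals plus at least 5 counted twice.
- The 18 URS cases are barred from new positions once the guide is in. Assuming all their pushes come after that, 122 − 18 = 104 remain, and 104/122 = 85%.
- An obstructing stone may be less free to fall. Leaving out the 22 Acute cases as well gives 104 − 22 = 82, and 82/122 = 67%.

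These are counts of cases in which repositioning is not barred. They are not counts of patients repositioned, for which the protocol gives no rate.

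**How large a shift is needed**

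Anything above 2 mm. The protocol gives no figure for a position-related shift. Purely as an assumption, a real or apparent shift of 3 to 10 mm would be 3/2 = 1.5 to 10/2 = 5 times the threshold with no push effect. The ratio only restates the assumption and is not evidence of bias.

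**The case against.** The strongest reply is that motion is assessed push by push. Each burst is watched in real time, images over each Push are saved, and patient and stone position are recorded. Most of the listed motion outcomes are defined per Push, and the second exam is meant to confirm location rather than to measure distance. After such a scheme, summing push displacements is at least as natural a reading of total distance as a start-to-end comparison. The formula for a descriptive total is also the sort of detail that a statistical analysis plan may hold.

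Much of this stands. A reader might infer that distance is taken only from session-level scans, or that the protocol does credit gravity-driven shifts to the device. It says neither; the text merely allows such shifts to count. A reader might also infer that average distance is inflated, but the listed average is for level 3 motions and is largely protected. Nor does the text support the inference that 85% of cases are affected, since repositioning is the last resort.

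Two parts of the reply do not settle the matter. First, the position records make separation possible, but no text says they will be used to remove displacement between pushes, and the blinded second reader confirms only representative movement. Second, the success metric is not left to another document. The protocol fixes it, and fixes it too loosely.

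It may also be said that a stone which pushes cannot move is unlikely to fall when the patient rolls. That limits the mechanism without removing it. Step e itself treats an unfavourable angle as a reason for failure, which is compatible with a free stone, and an apparent shift from a new scan plane needs no free stone.

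**Conclusion.** The concern holds in limited form. The 2 mm success metric, the percentage of stones moved and total distance per stone are worded loosely enough to count displacement from a change of posture or scan plane. Any such error favours the device, and the repositioning objective has no comparator. The per-push categories and level 3 distance are largely protected.

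The size cannot be derived. It depends on how often patients are repositioned and how far stones then shift or seem to shift, and the protocol gives neither; position-related shift is itself a plausible assumption that the protocol does not discuss. The 104 of 122 cases (85%) is a ceiling only, and rests on the URS pushes following guide insertion. It would be going too far to conclude that the primary objective is shown to be biased: in an early feasibility study without a stated hypothesis, the supported conclusion is that a success rule and a session-level distance need tightening before they are reported as device effects.

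**What to change.** In section 1.3:

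1. Replace the open-ended wording of the 2 mm metric with displacement of more than 2 mm seen during a Push, with subject and probe position unchanged.
2. Define total distance per stone as the sum of these within-push displacements, and take a new baseline stone position after each change of subject or probe position.
3. Use the pre/post exam comparison to call a stone moved or not moved only in sessions without subject repositioning, or where both exams were made in matched posture.

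The treatment procedure need not change. Step g already provides images over each Push and a record of patient and stone position, so this is mainly a change of text. The price is that reported distances and the percentage of stones moved may be somewhat lower.
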